7.1 Risks and benefits

Summary of known and potential risks and benefits, if any, to research participants.

7.2 Safety

Pleural interventional procedures will be performed as necessary as part of standard of care. Standard medical care and any drainage procedures (including needle aspiration, chest tube insertion or surgery) remains the responsibility of the treating physician of the patient. The patient will only be enrolled if a consultant physician feels it is safe to proceed.

7.3 Data and Safety Monitoring Board

The Data Safety Monitoring Board is set up to ensure the safety of study participants through study procedures, reviewing adverse events and serious adverse events and consider new data (recently published studies) that may determine the validity of study continuation. All deaths, anticipated or unanticipated, will be discussed with the DSMB. The committee determines whether significant benefits or risks have been uncovered which may have an impact on the feasibility and/or ethical conduct of the study. The DSMB will also help to ensure the scientific integrity of the study by reviewing the quality of the data it uses to make its decisions. The DSMB provides recommendations to the lead investigators, who oversees the study and determines whether the study should continue or be suspended or terminated.

7.4 Adverse Event (AE) Reporting

All AEs relating to the trial investigations, serious and non-serious, will be fully documented on the appropriate CRFs. For each AE, the investigator will provide the onset, end, intensity, treatment required, outcome, seriousness and action taken. The investigator will determine the relationship of the investigative procedure to all AEs as defined on the 'Adverse Event' CRF. The basis for judging the intensity of the AE as well as the causal relationship between the experimental procedure and the AE is described below.

An AE is defined as any untoward medical occurrence, including an exacerbation of a preexisting condition. It does not necessarily have to have a causal relationship with treatment. All AE's relating to the investigations occurring during the course of the clinical trial (ie; from signing the informed consent until death or the end of the study follow up period, whichever comes first) will be collected and documented by the investigator according to the specific definitions and instructions detailed in the 'Adverse Event Reporting' section of the Trial Master File. Cases will also be reported if a causal link between the AE and the trial investigations is suspected but not confirmed. Any event that meets the criteria for a Serious Adverse Event (SAE), as defined below, reported as an SAE.

A Serious Adverse Event (SAE) is defined as any AE that,

- results in death
- is life-threatening
- results in persistent or significant disability / incapacity
- prolongs hospitalisation by \geq 24 hours (i.e. unexpected overnight admission)
- is deemed serious for any other reason such that it is thought to jeopardise the patient and may require medical or surgical intervention to prevent one of the other outcomes listed in the above SAE definitions.

SAEs are to be reported immediately to the local ethics committee using the Serious Adverse Event Report Form including a documented causal relationship assessment and providing as much detail regarding the SAE as possible.

8 Data Management, Statistical Analysis and Record Keeping

8.1 Sample Size

This study will aim to recruit 50 participants with spontaneous (primary and secondary) pneumothorax and iatrogenic pneumothorax over 24-months. This number is achievable in the proposed timeframe and accounts for those who decline to take part in the study. The study may expand if major numbers are observed.

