4.3 Study Duration

The study will enrol participants for a period of 24 months. This is based on the number of potentially suitable participants seen in the recruiting centres (\sim 2/month).

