5.1 Source of Participants

This study will enrol 50 consecutive eligible patients with pneumothorax from the pleural service of Australian centres. A screening log will be maintained. Patients who require drainage/lung reinflation as part of their clinical care will be assessed before and after reinflation. All participants will receive standard care for their conditions as per their treating clinicians. From the time of signing consent, participants will remain in the study for 3 months.

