5.3 Participant exclusion criteria

- Pneumothorax with a concurrent pleural effusion > 1cm in size
- Hemodynamically unstable (systolic blood pressure of <90 mmHg, heart rate in beats per minute greater than or equal to systolic blood pressure in mmHg, respiratory rate of >30 breaths per minute, and Spo2 of <90% on room air)
- Age <18 years
- Mechanical limitations in bending forward (*e.g.*, spinal conditions or large abdominal mass)
- Pregnancy/lactation
- Inability to consent and/or comply with protocol

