5.4 Participant withdrawal criteria

Participants can withdraw at any time from the study and do not need to provide a reason. We will retain all participant data up until the time of withdrawal as outlined in the PICF. There may be reasons for the site PI to decide to withdraw a participant from the study. This could be due to inability to comply with the study protocol such as attending study visits or for other compliance issues. A participant may also be withdrawn in their best interests. In all cases, the study withdrawal form will be completed and a copy submitted to the lead site. Withdrawn participants will not be replaced. If considered clinically necessary, withdrawn participants will be asked to return to clinic for safety follow-up appointment(s).

6 Treatment of Participants

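### The only stated accrual rate, about 2 potentially suitable patients a month, leaves no room for the decliners that the target of 50 in 24 months is said to cover

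*Protocol*

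**What the plan says.** Three places in the protocol fix the recruitment plan.

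- Section 4.3 (Study Duration) sets the period: "The study will enrol participants for a period of 24 months". It gives the basis as follows: "This is based on the number of potentially suitable participants seen in the recruiting centres", with a rate of about 2 a month in brackets.
- Section 5.1 (Source of Participants) sets the number as enrolled patients, not patients approached: "This study will enrol 50 consecutive eligible patients with pneumothorax from the pleural service of Australian centres".
- Section 8.1 (Sample Size) repeats the target, "This study will aim to recruit 50 participants with spontaneous (primary and secondary) pneumothorax and iatrogenic pneumothorax over 24-months", and adds: "This number is achievable in the proposed timeframe and accounts for those who decline to take part in the study".

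The protocol gives no refusal, ineligibility or screen-failure rate and no number of centres. The figure in section 4.3 is the only accrual rate. Section 8.1 also says that the study may expand if numbers are large, but it says nothing about a shortfall.

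**The concern.** Section 8.1 makes a specific claim: 50 enrolled within 24 months, with refusals already allowed for. For that to hold, the centres must see more than 50 suitable patients in the period. The one rate given, multiplied by the one period given, comes to about 48. The patients in section 4.3 are described as potentially suitable and as seen at the centres, which is a count taken before consent. As worded, it cannot already be net of those who refuse.

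Feasibility is also the only reason offered for 50, since no precision or power argument appears. If the feasibility statement does not follow from its own inputs, the number has no stated support. The practical stake is a pilot that ends smaller than stated or runs longer than stated. Section 5.4 adds "Withdrawn participants will not be replaced". This does not change the recruitment count, but any later loss comes on top.

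**Working it through.** **Inputs**

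- Rate r: about 2 a month (section 4.3), read as the total over all centres.
- Period: 24 months (sections 4.3 and 8.1).
- Target: 50 enrolled (sections 5.1 and 8.1).
- Share d of patients seen who are not enrolled: not given. The values below are assumptions that show a range.

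**Step 1. Reproducing the plan's figure.** Supply = r × 24 = 2 × 24 = 48. Enrolling 50 needs 50 / 24 = 2.08 a month. With d = 0, 48 agrees with 50 within the rounding of the rate. The plan's figure is therefore reproduced only if nobody declines, whereas section 8.1 says decliners are covered.

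**Step 2. Allowing for losses at exactly 2 a month.**

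- Enrolled in 24 months = 48 × (1 − d)
- Rate needed for 50 in 24 months = 50 / [24 × (1 − d)]
- Months needed for 50 at 2 a month = 50 / [2 × (1 − d)]

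| Assumed loss d | Enrolled in 24 months | Rate needed per month | Months needed for 50 |
|---|---|---|---|
| 0% | 48 | 2.08 | 25.0 |
| 5% | 45.6 | 2.19 | 26.3 |
| 10% | 43.2 | 2.31 | 27.8 |
| 20% | 38.4 | 2.60 | 31.2 |
| 30% | 33.6 | 2.98 | 35.7 |

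**Step 3. Sensitivity to the rounding of the rate.** The highest rate that still rounds to 2 is about 2.49 a month. Supply = 2.49 × 24 = 59.8, about 60. The largest loss that still gives 50 on average = 1 − 50 / 59.8 = 0.16. So the most favourable rounding tolerates total losses of about 16%.

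**Step 4. Sensitivity to a per-centre reading.** If the rate were per centre, two centres would see 2 × 48 = 96. The tolerable loss would be 1 − 50 / 96 = 0.48, and the inconsistency would disappear.

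**Step 5. Effect on precision.** Half-width of a 95% confidence interval for a prevalence of 50% = 1.96 × √(0.25 / n):

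- n = 50: 13.9 points
- n = 38 (20% loss): 15.9 points
- n = 34 (30% loss): 16.8 points

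**The case against.** The strongest reply is that the rate is a one-figure approximation and should not be treated as exactly 2.00. That is right as far as it goes. A reader might infer that 48 against 50 is in itself an arithmetic error. The documents do not support this, because 2.08 a month rounds to 2 and gives 50. What rounding does not supply is the allowance for refusals, except within the limit in step 3, and the protocol states no such higher rate.

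Second, the study is multi-centre with no number of centres stated, so a per-centre rate is possible. The wording of section 4.3, "based on the number of potentially suitable participants seen in the recruiting centres", reads more naturally as a total. If per centre was meant, one added phrase resolves the matter.

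Third, a reader might infer that the rate is counted before all the exclusion criteria in section 5.3 and before the consultant's safety judgement in section 7.2, so that large further losses must follow. The text does not say so: suitability may already reflect some of the criteria. One of them, "Inability to consent and/or comply with protocol", is itself partly about consent, which blurs the line further. The point made here needs only the decliners.

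Fourth, the consequence is limited. Section 8.2 describes a pilot with descriptive statistics, estimation and modelling of correlations. No test is powered on 50, section 8.1 only aims at that number, and treatment is standard care in any case. This stands, and it lowers the priority of the point.

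**Conclusion.** The inconsistency is real but narrow. Read as a total, the protocol's only accrual figure supplies about as many patients as the target and so leaves nothing for the refusals that section 8.1 says are covered. With assumed losses of 5%, 10%, 20% and 30% at exactly 2 a month, about 46, 43, 38 and 34 would be enrolled in 24 months, or 50 would take about 26, 28, 31 and 36 months. These sizes rest on the total reading of the rate and on loss shares that are assumptions, not protocol figures.

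Two stronger conclusions do not follow. The documents do not show that the study will probably close short, since neither the true rate nor the consent rate is known. Nor do they show that consecutive recruitment is at risk: section 5.1 requires consecutive eligible patients and a screening log, section 8.3 includes everyone who qualifies and consents, and nothing suggests that either would be relaxed.

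At losses of 20% to 30% precision worsens by 2 to 3 points, which is modest for a pilot. This is a point that should be fixed, not one on which the study's validity turns.

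**What to change.** In sections 4.3 and 8.1:

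1. State whether the rate of about 2 a month is the total or per centre. If it is per centre, give the number of centres.
2. State whether it is counted before or after the eligibility criteria are applied.
3. Give the sponsor's own expected consent rate. The loss shares used in the check above are illustrations and should not be copied into the protocol.
4. Restate the target or the enrolment period so that rate × months × uptake gives the stated number, and add the expected confidence interval width for the prevalence of bendopnoea at that number.
5. If no uptake rate can be given, delete the clause in section 8.1 that claims decliners are covered.

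The change is to wording only. Its cost is that the stated duration may become longer or the stated sample size smaller.

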8.2 Statistical Plan

This is a pilot study to determine whether bendopnoea is present in patients with pneumothorax, and whether it correlates with clinical symptoms (pain and breathlessness), the size of the pneumothorax and respiratory physiological parameters. It also aims to determine whether bendopnoea is correlated with clinical outcome (i.e., response to drainage/lung reinflation).

Descriptive statistics of baseline characteristics of patients and measured bendopnoea, pain and breathlessness responses will be provided. The magnitude and direction of the change between the baseline and post-intervention measurements (e.g., responses in bendopnoea, pain and breathlessness) will be estimated. Statistical modelling will be applied to determine the correlation of bendopnoea to symptoms, the size of the pneumothorax, physiological parameters and clinical outcomes.

8.2 Statistical Plan Deviations

Procedures for reporting any deviation(s) from the original statistical plan (any deviation(s) from the original statistical plan should be described and justified in the protocol and/or in the final report, as appropriate). For further information refer to NHMRC "Reporting of Serious Breaches of Good Clinical Practice (GCP) or the Protocol for Trials Involving Therapeutic Goods" 2018.

8.3 Selection of participants for analyses

All patients who fulfil the criteria and consent for the study will be included in the analyses, to minimise/exclude selection bias. Our team includes experienced biostatistician [name] (University of Western Australia) for study planning and data analyses.

8.4 Data Management

8.4.1 Source Documents

Source documents provide evidence for the existence of the patient and substantiate the integrity of the data collected. Source documents are filed at the investigator's site. Data entered in the CRFs that are transcribed from source documents must be consistent with the source documents or the discrepancies must be explained (Source Document Verification). The investigator may need to also investigate any inconsistencies using medical records. These medical records will be available to the investigator as one of the patient's treating physicians.

8.4.2 Trial Master File (TMF)

A Trial Master File (TMF) will be created containing all the study documents including all ethics correspondence (emails and letters), and copies of the approved documentation for the study.

8.4.3 Data Sharing

De-identified data from paper case report forms is being transposed into the study REDCap database. The dataset will be exported for analysis at the end of the study from REDCap to an Excel spreadsheet for the designated study statistician. Consent to this study is extended so data collected from this study will be used in future related studies such as meta-analysis study involving other studies of the PLEASE series. Those wanting access will need to contact the study CPI and provide an outline of the reason that data access is required. If this is deemed legitimate an amendment will need to be made to state that the data are to be made available to the individual and include the institution where the data will be held and archived. Where possible a virtual transfer of data will be made so that the primary dataset remains at the original institution and is managed according to local guidelines.

8.4.4 Data Archival

Data anonymisation is carried out at source. Data cleaning is carried out following data lock at the end of the study and following completion and resolution of all data queries. The cleaning is essentially carried out by the nominated statistician.

The long-term storage is onsite. If these buildings are to be used for other reasons or the building are to be pulled down, then the backup position would be archive with Iron Mountain

and set up a contract accordingly. Standard operating procedures (SOPs) for archiving paper records/ and TMF will be followed. An electronic archive of the study will also be created and retained in a named access only section of the SCGH W drive. The study data will be retained for 15 years.

9 Monitoring / Audit

The study investigators/institutions will permit trial-related monitoring, audits, and regulatory inspections, providing direct access to source data/documents. This may include, but is not limited to, review by external sponsors, Human Research Ethics Committees and institutional Governance review bodies.

This study will have site monitoring carried out by the lead site. Source data will be scrutinised to ensure the provision of robust data. Data entered in the CRFs that are transcribed from source documents must be consistent with the source documents or the discrepancies must be explained. Any discrepancies should be resolved with the site PI or otherwise documented as File Notes. Procedure deviations and or violations may be determined at this time and will need to be reported according to local procedure/policy. Source documents are filed at the investigator's site.

10 Quality Control and Quality Assurance

10.1 Data Quality Control and Reporting

After data have been entered into the study database, a system of data validation checks will be implemented and applied to the database. The study database will be updated in accordance with the resolved query reports. All changes to the study database will be documented.

10.2 Data Quality Assurance

The study will be conducted according to the principles of ICH GCP, National Statement and local SOPs The accuracy of the data will be verified by comparing study data to source documents. Medical records and progress notes will be kept accurate and up to date and available at all times for inspection in the event of an audit.

11 Ethics

The study will not be initiated before the clinical trial protocol and informed consent and patient information form have been reviewed and received approval/favourable opinion from the local Human Research Ethics Committee (HREC) and other regulatory authorities as required by local laws and regulations. Should a protocol amendment be made that needs HREC approval and authority notification/approval, the changes in the protocol will not be instituted until the amendment and revised informed consent (if appropriate) have been reviewed and received approval / favourable opinion from the local HREC and other regulatory authorities as required by local laws and regulations. A protocol amendment intended to eliminate an apparent immediate hazard to participants may be implemented immediately providing that the regulatory authority and HREC are notified as soon as possible and an approval is requested. Protocol amendments exclusively for logistical or administrative changes may be implemented with notification only of the HREC and other regulatory authorities as required by local laws and regulations.

12 Budget, Financing, Indemnity and Insurance

Funding will be sought from grant funding bodies to cover staffing time for study administration. The relevant contracts will be signed as separate documents to the protocol. Other time is given in kind as approved by the relevant heads of department. Any shortfalls in funding will be covered by CPI-[name]'s research funds at the Institute for Respiratory Health.

13 Publication

No study results will be formally published prior to completion of the final HREC study report.

14 Appendices

Study Flowchart

Trial entry, trial treatment and post procedure care.

Trial Entry

- 1. Participants with pneumothorax referred for assessment, and/or air drainage (as part of standard clinical care for management of pneumothorax).
- 2. Fulfil inclusion and exclusion criteria.
- 3. Written informed consent.

Study Protocol - pre intervention

- 1. Baseline assessment.
- 2. Study procedures undertaken pre intervention.
